CLINICAL TRIAL PROTOCOL

METABOL_EMAIL

ENGLISH VERSION

Electronic mail to clinic team, advising treatment modifications due to low metabolic indexes of 75+ years old patients: Effect on health measures.

Principal Investigator: [name]

Clalit Health Services

[name].

[contact]

Protocol Version #3 13/10/2015

Translated From Hebrew To English

Investigators:

[name], PhD; [name]; [name], MPA, RN; [name], RN ; [name], BSc, MHA ,RD; [name]; [name].

Background:

Technologic progress promotes large scale medical monitoring and intervention. It enables increased attention to signs of nutritional deficiency. Notable examples include the monitoring of Body Mass Index (BMI), glycated hemoglobin (HbA1c%) and total serum cholesterol (herein referred to as cholesterol), which are integrated in the system of quality measures today (e.g. the Israeli National Program for Quality Indicators in Community, 2012). Monitoring and correcting caloric nutritional deficiencies are critical for optimal medical and nursing care, certainly at ages of 75 years and more (Hazzard's, 2009; Brunner & Suddarth's, 2013).

Interactions between diseases, nutritional status and medical treatment are particularly complicated with advancing age. Old age often comes with multiple morbidity as well as increased vulnerability to medicine adverse effects. These may result in nutritional imbalance, which is detrimental to health and to daily living functions. Malnutrition is a major cause of vulnerability to stress (frailty). Intriguingly, medicines that may harm the digestive system and nutritional status include those that are used frequently to improve 'quality indicators'. Examples include metformin, statins and many more.

Hence, when monitoring health quality indicators, the authors believe it is important to search for optimal values - that include minimum levels (and not only maximum levels) for each physiologic indicator. In this trial, we will focus on BMI, HbA1c% and cholesterol.

BMI is a widely used as an index of nutritional problems. In a meta-analysis which included 2.88 million people, the optimal BMI for overall survival was found to be 25-30 kg/m² (Flegal, 2013; Dixon, 2014 ; Pan, 2012). Rapid weight loss is a strong indicator for health and functional decline. Such a weight loss, especially with low BMI values, usually mandates investigation in order to eliminate the cause or to limit its effect. A use of an automatic e-mail alert system was found to improve screening rate of malnourished patients in hospital (Giovannelli, 2014).

Correlation between death and HbA1c% is U-shaped, with increased mortality under a 6.5% level in patients taking two antidiabetic medicines (Currie, 2010). Among these patients, the optimal HbA1c% values of for survival were 7.5-8%. A substantial proportion of older adults with diabetes were found by Lipska et al. (2015) to be potentially overtreated.

Correlation between death and cholesterol is also U-shaped (Iso, 1989). Hypocholesterolemia is defined as cholesterol below 160 mg% and predicts increased mortality and morbidity (Hazzard's, p. 1341). We found no interventional study for this situation in the scientific literature.

In our experience, Email alerts to doctors, regarding an over-tight control of specified diabetic patients by sulphonyl-urea medicines was followed by a reduction (from 3% to 1.8%) in

mortality comparing to a previous-year matched control group (unpublished observations). While this result was not statistically significant, it encouraged us to try this large scale interventional clinical trial. It also served us in assessing the size of the study population needed.

Objectives:

This study aims to determine whether reminding physicians and nurses about too low values of weight (as BMI), glucose (as HbA1c%) or cholesterol (as total serum cholesterol) improves survival and health of people older than 75 years.

Study Hypotheses:

A. Main Study Hypotheses:

1. Compliance: Sending the intervention letter will cause a positive change in the relevant index (a rise in BMI, HbA1c%, or cholesterol, respectively).
2. Health effect: Sending the intervention letter will cause a lower mortality rate in each study group compared to control groups, within a year.

B. Other Study Hypotheses: compared to control groups, sending the intervention letter will cause improvement in morbidity and in secondary measures (see below).

And in detail:

Reducing numbers of hospital stays and days of stays, numbers of physician and nurse visits with records of symptoms, number of dispensed medicines, medical expenses; in the HbA1c% intervention - reduced number of dispensed anti-diabetes medicines and reduced rate of measuring glucose levels of 70 mg/dL or less ; in the cholesterol intervention - reduced number of dispensed anti-cholesterol medicines.

Increasing rate of weight measuring, BMI level, HbA1c% measuring, HbA1c% level, cholesterol measuring, cholesterol level; in the BMI intervention - percentage of patients evaluated by a nurse and counseled by a dietician.

Methodology:

Briefly: This prospective, randomized controlled trial, will compare BMI, HbA1c% and cholesterol values, rate of death, number of stays, days of stays, numbers of physician and nurse visits with records of symptoms such as "weakness", "dizziness" and total medical expenses of patients 75 years and older that their clinic staff will receive the email concerning them, versus patients that such email concerning them will not be sent. The trial has 3 different alerts: 1. An alert about a significant drop in BMI; 2. An alert about low HbA1c% level in patients treated with diabetes medicines; and 3. An alert about hypocholesterolemia in patients treated with cholesterol-lowering medicines.

Recruiting and inclusion criteria: 75 years and older at the beginning of the trial, clients of Clalit health Services at the North and the South districts, which will be identified thru the computer system (BO) as having one or more of the following:

For alert no. 1: A drop in BMI of 2 Kg/m² or more during the last two years and¹ a BMI lower than 23 Kg/m² and¹ no dietician counseling during the last year.

For alert no. 2: HbA1c% of 6.5% or less and¹ dispensing diabetes medicines during the last 2 months.

For alert no. 3: Total cholesterol less than 160 mg/dL and¹ dispensing cholesterol-lowering medicines during the last 2 months.

Exclusion criteria:

General: Clients that an email address of their physician or nurse is not found.

For alert no. 3: Clients with a diagnosis of myocardial infarction, ischemic heart disease, transient ischemic attack or cortical cerebrovascular accident.

Study schedule:

Sending the alerting mails will be done in one-session during 2015.

Collecting the data will be done after one year.

Publishing the main results will be done within another year at the latest (2017).

Study procedures and methods:

0. Preparations:

A pre-trial email will be sent to the primary physicians on behalf of the district managements in order to inform about the trial. The text is provided in appendix No. 4. Feedback regarding receiving of the letter (full email boxes etc.) will be collected. Primary physicians would be able to choose to refrain from participating.

1. Finding the participants:

A. By using the Clalit health services computer system; an Excel table will be created; which will include these fields: Identity number; Name; Age; Sex; Clinic name; Primary physician name; Primary physician's email address; Nurse in charge at the clinic; email address of that nurse; Last BMI value of the last year; First BMI value of the previous year; Existence of a dietician visit on the last year; Last total cholesterol level; Whether dispensing of a cholesterol lowering medicine was recorded during the last 2 months; Name of (the last) cholesterol lowering medicine dispensed - with dose and quantity; Whether dispensing of a diabetes medicine was recorded during the last 2 months;

¹ AND as intersection

Name of (the last) diabetes medicine dispensed - with dose and quantity; Whether diagnosed with myocardial infarction; Whether diagnosed with brain infarction; Whether diagnosed with any cardiovascular disease.

B. Participants for each separate inclusion group, according to the criteria above, will be identified. At this stage, a new list will be created, where the people who don't fit any of the criteria will be excluded. Some of the participants may fit more than one criterion. Hence 7 subgroups are created:

- A) Patients that fit only alert 1. (Significant weight loss without dietitian assessment)
- B) Patients that fit only alert 2. (A potentially too tight medicinal diabetes treatment)
- C) Patients that fit only alert 3. (A potentially too tight medicinal cholesterol lowering)
- D) Patients that fit both alert 1. and alert 2.
- E) Patients that fit both alert 1. and alert 3.
- F) Patients that fit both alert 2. and alert 3.
- G) Patients that fit all alerts: 1. , 2. and 3.

C. Population size: According to 11.2014 there are about 5000 patients that fit these criteria at North district and a similar number at the South district, totaling ~ 10,000. This provides a sufficient statistical power to examine the effect on the main hypotheses. (We used Pearson χ^2 test, assuming a 3% to 1.8% decline in death rates, as observed in a similar setting).

2. Randomization:

- a. Randomization aims to get an unbiased and equal division into an intervention group and a control group.
- b. Randomization will be via computer: by adding a column in the excel table, with the function =ROUND(RAND(),0). This means 1:1 randomization to 0 (control) or 1 (intervention letter).
- c. In order to avoid large differences in numbers of participants among the subgroups, the randomization procedure will repeat until the difference between control and intervention group is less than 2%.

3. The alert emails will be prepared and sent via "Mail Merge" (of Microsoft Word) to the primary physicians and to the nurses in charge at the same clinics. The templates to those emails are shown in the appendix. Technical problems (e.g. full mailbox of recipients) will be recorded and managed promptly (- days, hopefully), by the principal investigator.

4. Collecting outcome data: will be via the Clalit health services computer system. Data will include:

a. For all participants (control and trial groups), for the year that follows the intervention email:

1. Mortality (of any cause)
2. Days in stays (of any ward)
3. Number of stays
4. Number of physician visits
5. Number of nurse visits with symptoms
6. Number of all medicines dispensed
7. Medical expenses
8. Last BMI level and date
9. Last cholesterol level and date
10. Last HbA1c% level and date
11. Glucose levels of 70 mg/dL or less, and dates

b. For alert 1., for the year that follows the intervention email:

1. Recording of functional estimation by a nurse
2. Recording nutritional estimation by a nurse
3. Recording dietitian consultation

c. For alert 2. on the 3 months that follows the intervention email:

1. Whether a diabetes medicine was dispensed, and if so:
2. Name of diabetes medicine, dose and quantity

d. For alert 3. on the 3 months that follows the intervention email:

1. Whether a cholesterol lowering medicine was dispensed, and if so:
2. Name of medicine, dose and quantity

5. Data security: will be handled according to Clalit health systems procedures. The information will be saved in allowed secure servers only and will be available to authorized researchers only after their guidance and signing a non-disclosure commitment. When applicable, personal identification details will be omitted from the lists.

6. Outcome analysis:

Categorical variables will be shown as frequencies and percentages. Continuous variables will be shown using standard distribution indices (e.g. average, standard deviation, median, etc.). Differences between the arms of the study will be examined using Chi-square test (or Fishers' exact test) for categorical variables and T-test (or Wilcoxon two sample test) for continuous variables. The statistical processing will be performed using Excel or SAS 9.2 software and will be statistically significant if $P < .05$.

7. Ethical issues of the trial:

A waiver of the requirement to obtain a signed informed consent from participants is requested with the following reason: There is no contact with the patients, only unsheathing their existing data.

A waiver of Form 11 is requested with the following reason:

The family physician will be the one who would get the alert related to this trial in the first place.

Appendixes:

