This letter is sent to you as a part of an authorized clinical trial. Details about the trial can be found in [this link](#). **Briefly:** Patients aged 75+ with signs of a metabolic risk were found via computer. This detection included **low HbA1c% (<6.5%) with anti-diabetic medicines**, etc. After randomization to control and intervention groups, relevant alerts are sent for the intervention groups. In this trial we will check the effect of these alerts on treatment, health indexes and survival – a year from now.

Mrs./Mr. _____ , I.D. _____, at _____ clinic of yours, was lately found to take anti-diabetic medicine (_____) and the HbA1c% was _____. This level is low for diabetic medical treatment. According to current guidelines and quality-indicators, a level somewhat below 8% is satisfying and safer.

We ask you to consider **re-estimation** of his functional and medical condition and of his treatment, including **lowering the dose of the anti-diabetic medicine**.

We will be grateful for cooperation and will be happy to discuss any questions,

Sincerely,

[name] (Principal investigator)

[name]

[contact]

[contact]

Further background:

Correlation between death and HbA1c% is U-shaped, with increased mortality under the level of 6.5% in patients taking two antidiabetic medicines (Currie, 2010). Among these patients, the optimal HbA1c% values of for survival were 7.5-8%. Updated quality-measures consider <8% is satisfying for diabetic patients of age 75+ years.

Appendix 3. Template for email regarding a patient with low cholesterol that took a cholesterol lowering medicine.

Email Subject:

LIMIT-C trial alert: Low cholesterol level of your patient – Mrs./Mr. _____ , I.D.

Email Body:

Dear Dr./Mrs./Mr. _____ ,

This letter is sent to you as a part of an authorized clinical trial. Details about the trial can be found in [this link](#). **Briefly:** Patients aged 75+ with signs of a metabolic risk were found via computer. This detection included **low cholesterol (<160mg%) with cholesterol lowering medicines**, etc. After randomization to control and intervention groups, relevant alerts are sent for the intervention groups. In this trial we will check the effect of these alerts on treatment, health indexes and survival – a year from now.

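### Any rise in HbA1c% counts as a positive change, and no prespecified analysis separates a rise within the protocol's cited range from a rise above 8%

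*Combined protocol and SAP*

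**What the plan says.** **Direction of success.** Study Hypotheses, A.1 (compliance): "Sending the intervention letter will cause a positive change in the relevant index (a rise in BMI, HbA1c%, or cholesterol, respectively". The detailed list under B repeats the direction: "Increasing rate of weight measuring, BMI level, HbA1c% measuring, HbA1c% level, cholesterol measuring, cholesterol level". Neither place gives an upper bound or a target range.

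**Rationale.** The Background argues that indicators need minimum as well as maximum values. For HbA1c% it says "Correlation between death and HbA1c% is U-shaped" and, for patients on two antidiabetic medicines, "Among these patients, the optimal HbA1c% values of for survival were 7.5-8" per cent. The alert 2 email (Appendix 2) tells clinicians that "a level somewhat below 8% is satisfying and safer", and its further background adds: "Updated quality-measures consider <8% is satisfying for diabetic patients of age 75+ years". The same email asks them to consider reducing the anti-diabetic dose. Patients enter alert 2 at "HbA1c% of 6.5% or less".

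**Data and analysis.** Section 4 collects, for all participants over the following year, the last HbA1c% with its date (item a.10), all-cause mortality, hospital stays and days, visits and expenses. The only glucose item (a.11) is "Glucose levels of 70 mg/dL or less, and dates". Section 6 gives descriptive summaries (mean, SD, median) and between-arm tests: chi-square or Fisher for categorical variables, t-test or Wilcoxon for continuous ones. It names no threshold or range for HbA1c%.

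**The concern.** On the protocol's own U-shaped account, a rise from 6.3% to 7.4% and a rise from 6.3% to 9.5% are different events. Under hypothesis 1 both are positive, and in a comparison of means the second counts for more. Because the email invites a lower dose, its main foreseeable risk lies on the high side, whereas the one glucose item looks only at the low side, where benefit is expected.

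What is at stake is the reading of a significant compliance result. It could reflect many patients moving modestly, or a minority moving well past 8%. Without a prespecified comparison, any look above 8% is optional and post hoc.

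**Working it through.** The plan gives no figure on this point to reproduce. Its only sample-size statement concerns mortality, and nothing here depends on it. The documents give no HbA1c% distribution, overshoot rate or alert 2 group size, so every input below is an assumption unless a source is named.

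**1. Same mean, different tails.**

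- From the documents: entry at 6.5% or less; reference level 8%.
- Assumed: baseline drawn from a normal distribution with mean 6.1 and SD 0.3, values above 6.5 set to 6.5; follow-up noise SD 0.4; mean rise 0.4 points.
- Without any rise, simulated follow-up has mean 6.09 and SD 0.49.

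If a share q of patients rises by r, with q × r = 0.4:

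- mean = 6.09 + 0.4 = 6.49
- SD = √(0.49² + q(1 − q)r²)
- share above 8% ≈ q × P(Z > (8 − 6.09 − r)/0.49) + (1 − q) × P(Z > (8 − 6.09)/0.49), where the second term is negligible.

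For q = 20% and r = 2.0, the share is 0.20 × P(Z > −0.18) = 0.20 × 0.57 = 11.4%, and the SD is √(0.24 + 0.16 × 4) = 0.94. Simulation gives:

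| Pattern | Mean | SD | Median | Above 8% |
|---|---|---|---|---|
| No rise | 6.09 | 0.49 | 6.09 | about 0 |
| All rise 0.4 | 6.49 | 0.49 | 6.49 | 0.06% |
| 30% rise 1.33 | 6.49 | 0.78 | 6.36 | 3.5% |
| 20% rise 2.0 | 6.49 | 0.94 | 6.25 | 11.5% |
| 10% rise 4.0 | 6.49 | 1.29 | 6.16 | 10.0% |

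Drawing the baseline from a truncated distribution, instead of setting high values to 6.5, gives 0.03%, 2.8%, 10.9% and 10.0% above 8% for the four rise patterns.

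**2. Can the tail alone make hypothesis 1 significant?** Assume a control mean of 6.1 and SD 0.5 to 0.8, two-sided 5% level. Suppose 5% of intervention patients move to 9.0% and nobody else changes.

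- Mean difference: 0.05 × (9.0 − 6.1) = 0.145.
- Intervention SD: √(0.5² + 0.05 × 0.95 × 2.9²) = 0.81, or 1.02 for SD 0.8. Averaging the variances of the two arms gives an SD of 0.67 or 0.92.
- t-test, 500 per arm: SE = 0.67 × √(2/500) = 0.042; 0.145/0.042 ≈ 3.4; power ≈ Φ(3.42 − 1.96) = 93%. With SD 0.8 it is 71%.
- t-test, 1,000 per arm: 94% to 99.8%.
- Wilcoxon: P(intervention value > control value) ≈ 0.5 + 0.05 × 0.5 = 0.525. With z ≈ 0.025 × √(6n), z = 1.37 at 500 and 1.94 at 1,000 per arm, so power is about 28% and 49%.

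**3. Is the proposed comparison informative?** Illustrative power for a difference in the share above 8%: 1% against 3% gives 62% at 500 per arm and 89% at 1,000; 2% against 4% gives 46% and 75%. For 1% against 3%, the 95% half-width is 1.96 × √(0.01 × 0.99/n + 0.03 × 0.97/n), which is 1.7 points at 500 per arm and 1.2 at 1,000. An interval is therefore more useful than a bare test.

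**The case against.** Four points count on the other side.

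- **A reader might infer that overshoot could not be seen as harm. The documents do not support that.** Item a.10 keeps the last HbA1c% at any level in both arms, and mortality and hospital stays are compared. What is missing is a prespecified analysis, not the HbA1c% data.
- **A reader might take 8% as the trial's ceiling. It is not one.** The 7.5-8% range is a cited survival optimum in a particular group of patients, and the level below 8% in the email is described as satisfactory under guidelines and quality measures. Neither is set as a trial safety limit.
- **Hypothesis 1 is labelled compliance.** All alert 2 patients start at 6.5% or less, so a rise is a natural sign that clinicians acted. Health effects are tested separately, and the plan nowhere says it will conclude that control improved. This stands, but the list under B does place a higher HbA1c% level among improvements.
- **The planned summaries would hint at a tail.** In the illustration, the uniform rise and the 20% pattern differ in SD (0.49 against 0.94) and median (6.49 against 6.25), and a Wilcoxon test reacts less to a small extreme group. This also stands. However, section 6 does not say when the t-test and when the Wilcoxon test applies, and neither test nor those summaries gives the share above 8%.

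**Conclusion.** The point holds as a gap in prespecification. The plan counts a rise in HbA1c% as positive without an upper bound, its rationale says that more is not always better, and no planned comparison separates the two kinds of rise. Under the assumed inputs, one mean rise of 0.4 points goes with anything from about 0.1% to 11.5% of patients above 8%, and a significant t-test could arise wholly from values above 8%. These sizes are illustrations: the patterns are invented, and a group rising by 4 points is extreme. That the mean alone does not determine the share above 8% does not depend on them.

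Two limits of the data remain: only the last HbA1c% is kept, so an earlier excursion can be missed, and high spot glucose is not extracted. This is an inexpensive improvement that should be made; it does not show that the trial would overlook harm.

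**What to change.** 1. Keep the between-arm comparison of HbA1c% levels as the compliance measure. In Study Hypotheses A.1 and the list under B, describe it as a process measure, not as improvement in itself.
2. In section 6, prespecify for all patients who meet the alert 2 criterion (subgroups B, D, F and G) a table by arm of the last HbA1c% from item a.10: 6.5% or less; above 6.5% to 8%; above 8%; not measured.
3. Report the between-arm difference in the proportion above 8%, with its 95% confidence interval, as a harm outcome. State the denominator and show the not-measured row, because the protocol expects the letter to change how often HbA1c% is tested.
4. State that 8% is the protocol's own cited figure, used for reporting only and not as a clinical rule.

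The cost is a few sentences and one extra table, with no new HbA1c% data. The compliance result may read less favourably, and the table will not capture excursions before the last value.

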Mrs./Mr. _____ , I.D. _____, at _____ clinic of yours, was lately found to take cholesterol lowering medicine (_____) and the total cholesterol was _____. This level is low. (Hypocholesterolemia is defined when levels fall below 160mg%.)

We ask you to consider **re-estimation** of his **functional** and **medical** condition and of his treatment, including **lowering the dose of the cholesterol-lowering medicine**.

We will be grateful for cooperation and will be happy to discuss any questions,

Sincerely,

[name] (Principal investigator)

[name]

[contact]

[contact]

Further background:

In old age, a total cholesterol level of **less** than 160mg% is related to a **greater risk** of functional decline and of death. Cholesterol level may be low due to a combination of factors, including **reversible** ones, such as bacterial **infection**, **smoking**, **malnutrition**, medicines and more. Cholesterol lowering **medicines** may cause nutritional insult and revising their dose and usage is warranted, especially with patients older than 75 years, and particularly if they suffer from possible adverse effects of these medicines. Adverse effects include: musculo-skeletal - pain and gait problem, liver, digestive and respiratory tract symptoms and mental problems such as insomnia, depression etc.

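### For alerts 2 and 3 the stated drug outcome counts medicines, so it may not register the dose reduction that the letters name, and the dose data collected have no outcome

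*Combined protocol and SAP*

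**What the plan says.** **Requested action.** The letter in Appendix 2 asks the clinician to consider reassessing the patient's condition and treatment, including "lowering the dose of the anti-diabetic medicine". The letter in Appendix 3 does the same, including "lowering the dose of the cholesterol-lowering medicine".

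**Stated drug outcomes.** Study Hypotheses, part B, gives "in the HbA1c% intervention - reduced number of dispensed anti-diabetes medicines" and "in the cholesterol intervention - reduced number of dispensed anti-cholesterol medicines". It does not say whether the number is of distinct medicines, dispensings or units, or over what window it is taken. No hypothesis mentions dose.

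**Baseline data.** Study procedures, item 1.A, lists "Name of (the last) diabetes medicine dispensed - with dose and quantity" and "Name of (the last) cholesterol lowering medicine dispensed - with dose and quantity". Only one medicine per class is held.

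**Follow-up data.** Collecting outcome data (item 4), lists c and d, record over the 3 months after the email whether a medicine of the class was dispensed and, if so, "Name of diabetes medicine, dose and quantity" (alert 2) or "Name of medicine, dose and quantity" (alert 3). The only medicine count in the follow-up lists is in list a. It covers one year and all medicines together, not by class.

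**Main compliance outcome.** Hypothesis A.1 is a rise in the relevant index, that is HbA1c% for alert 2 and cholesterol for alert 3.

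**Analysis.** Outcome analysis (item 6) compares the arms, using a chi-square or Fisher's exact test for categorical variables. It mentions neither change from baseline nor dose.

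**The concern.** The named action and the stated drug outcome are on different scales. A clinician who lowers the dose of a patient's single diabetes medicine has done what the letter suggests. If distinct medicines are counted, that patient still scores one, the same as a patient whose clinician ignored the email.

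Dispensing is the most direct record of what clinicians did. HbA1c% and cholesterol are seen only in patients who are retested, and part B itself expects the letter to increase testing, so the index may be observed selectively by arm. Dispensing needs no retest. If mortality does not differ, a dose-based outcome would help to separate clinicians not acting from action not helping. A count separates them poorly. The data to do better are already mostly collected, but the plan does not say how they will be used.

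**Working it through.** There is no plan figure to reproduce. The only power statement (item 1.C) concerns mortality and is not affected by this point.

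**Step 1. What each meaning of *number* does with a dose-only response.**
- Distinct medicines: the count is the same before and after, so the contribution is 0.
- Dispensings or units: a lower dose may or may not change the count, depending on how it is dispensed. The plan does not settle this.

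**Step 2. Size of the dilution if distinct medicines are counted.** Let r be the excess share of letter-arm patients whose treatment is changed, and s the share of those changes that are dose-only. The other changes each stop one medicine. The mean difference in count is d = r × (1 − s), so the count keeps the fraction 1 − s of the response: 50%, 25%, 10% and 0 at s = 50%, 75%, 90% and 100%. The documents give no value for s.

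**Step 3. Illustration of what this does to power.** Every input is assumed: SD of the class-specific count 0.8, two-sided 5% level (the plan gives P < .05 without sidedness), and n per arm for one alert of 500, 1,500 or 2,500. The plan gives about 10,000 patients in total but no split by alert.

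SE = 0.8 × √(2/n), and power = Φ(d/SE − 1.96). Example with n = 1,500, r = 20%, s = 50%: d = 0.20 × 0.5 = 0.10; SE = 0.8 × √(2/1,500) = 0.0292; 0.10/0.0292 = 3.42; 3.42 − 1.96 = 1.46; power 0.93.

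| r | s | d | n = 500 | n = 1,500 | n = 2,500 |
|---|---|---|---|---|---|
| 20% | 0 | 0.20 | 0.98 | >0.99 | >0.99 |
| 20% | 50% | 0.10 | 0.51 | 0.93 | 0.99 |
| 20% | 75% | 0.05 | 0.17 | 0.40 | 0.60 |
| 20% | 90% | 0.02 | 0.06 | 0.10 | 0.14 |
| 10% | 0 | 0.10 | 0.51 | 0.93 | 0.99 |
| 10% | 50% | 0.05 | 0.17 | 0.40 | 0.60 |
| 10% | 75% | 0.025 | 0.07 | 0.14 | 0.20 |

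At s = 100% there is no difference in count to detect.

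**Step 4. The same response scored as stopped or reduced.** Here the difference between arms is r whatever the value of s. With an assumed 5% in the control arm, the smallest case above (r = 10%, n = 500) compares 15% with 5%. SE = √[(0.15 × 0.85 + 0.05 × 0.95)/500] = 0.0187; 0.10/0.0187 = 5.35; 5.35 − 1.96 = 3.39; power above 0.99. This takes the classification as accurate; misclassification, for example from refill timing, would lower it.

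**Step 5. Can that outcome be formed from the listed fields?** Only in part. Baseline holds the last medicine of the class, and lists c and d are worded in the singular. A patient on two diabetes medicines (the group behind the 6.5% evidence cited in the Background) cannot be judged medicine by medicine. The windows also differ: dispensing in the last 2 months before the email, and 3 months after it. Unscaled, steady treatment would show 3/2 = 1.5 times the baseline amount, and a cut by one third would show 2/3 × 3/2 = 1, that is, no change.

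**The case against.** The strongest reply is that the letters ask for reassessment of treatment and give a lower dose as something included in it. Stopping a medicine also fits the request and lowers the count. This stands. A reader might infer that compliance with the letter leaves the outcome unchanged, but that requires both that distinct medicines are counted and that every response is dose-only. The documents establish neither.

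Second, hypothesis A.1 is labelled compliance and is measured by the index, which can respond to a dose change. This stands too. A reader might infer that the trial misses the requested action altogether. It does not, although the index is available only for retested patients.

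Third, the lack of a baseline count may look like a source of bias. It is not. The planned comparison is between randomized arms, and no change score is proposed. What is lost is the ability to classify response and to adjust for baseline. An insensitive count gives a smaller true difference, not a biased estimate of it.

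Fourth, a reader might infer that clinician response cannot be linked to HbA1c%, cholesterol or mortality. For the recorded medicine it can, since name, dose and quantity are extracted before and after the email. What is missing is a pre-specified definition.

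Finally, the retained fractions follow directly from the assumption that dose-only changes score zero, and the shares are not from the documents. That is correct. They show the mechanism and do not predict its size.

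What survives is that the one drug change named in the letters has no defined outcome, and that on the most natural reading of *number* the stated outcome gives it no weight.

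**Conclusion.** The point holds for the secondary drug hypotheses of alerts 2 and 3 and no further. If distinct medicines are counted, the between-arm effect is diluted to the fraction 1 − s. In the illustration with 1,500 per arm and 20% of patients changed, power falls from above 0.99 to 0.93, 0.40 and 0.10 at dose-only shares of 50%, 75% and 90%. These figures rest on an assumed SD, group size, response rate and dose-only share. If dispensings or units are counted, the effect of a dose reduction is undetermined. Mortality, the main index outcomes and alert 1 are untouched. The change is worth making because a better outcome can be built mostly from data that the plan already collects.

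**What to change.** In hypothesis B, for alerts 2 and 3, add the outcome of any class medicine stopped or reduced, and compare its share between arms with the chi-square test already planned.

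- Judge it medicine by medicine, on dispensed dose × quantity per day, scaled for the 2 months before and the 3 months after the email. Do not sum different drugs.
- State in advance how large a fall counts as reduced, since refill timing alone moves the dispensed amount, and how a replacement within the class is scored.
- Report patients who die within the 3 months separately, so that they are not classed as stopped or reduced.
- In 1.A, c.2 and d.2, extract all medicines of the class, not only the last one, and say that this is done in both arms.
- Keep the count as a supportive result, with its unit and window defined.

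The cost is a somewhat wider data query at both time points, protocol wording and a little more analysis. No dose or clinical rule is proposed.
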